2.3 Exploratory

2.3.1 Exploratory objectives

- Pharmacogenomics: to evaluate impact of ACSS score for association with toxicity and efficacy in HiDAC 123 arm
- Describe RR, LFS and OS in each cohort

2.3.2 Exploratory endpoints

- Record pharmacogenomic profiles if results available from next generation sequencing (NGS)/GatorSeq on bone marrow (BM) biopsies for both arms (collected at diagnosis as standard of care).
- Compute ACSS SNP score using the genotype data for subjects in HiDAC 123 arm. We will genotype SNPs of relevance and based on the ACSS score classify into two groups having ACSS score ≥ 0 or <0 . ACSS score will be evaluated for association with certain endpoints (duration of neutropenia, thrombocytopenia, RR and OS). Peripheral blood samples will be collected and analyzed through [name] lab at the University of Florida and NGS results will be used to calculate the ACSS score.
- Describe relapse rate (RR). Relapse rate defined as incidence of confirmed relapse by peripheral blood flow or bone marrow biopsy results. Patients will be monitored up to 48 months after starting induction and will be reported if available.
- Describe overall survival (OS) and leukemia-free survival (LFS). Overall survival defined as the time from date of complete remission (CR) to death from any cause. Leukemia-free survival defined as time from CR to AML relapse or death, whichever comes first. Cause of death will be recorded. Patients will be monitored up to 48 months after starting induction and will be reported if available. These are not expected to be different between the two cohorts.^{1,2}
- Examine minimal residual disease (MRD) positivity after recovery from induction prior to study entry. The following modalities on bone marrow biopsy and aspirate will be used: flow cytometry (FC), karyotyping utilizing cytogenetics (CG), and fluorescence in situ hybridization (FISH). Patients with evidence of disease by any technique above will be classified as being MRD_{pos}. FC will be performed on bone marrow specimens using monoclonal antibodies either as a large panel if the patient was newly evaluated or as a limited but targeted panel based on previously known patient-specific leukemia immune phenotype. MRD will be reported as a percentage of CD45 positive white blood cells (WBCs) and will be labeled MRD_{pos} if leukemic cells account for $\geq 0.1\%$ of the analyzed total WBCs. CG will be performed using standard G-banding methods on 20 metaphase cells. FISH will be reported as a percentage of abnormal nuclei among the examined 300 interphase nuclei. MRD_{pos} by CG will be defined as abnormal karyotype seen in at least

two metaphase cells, or less than two cells if it was a previously known abnormality for the given patient. FISH positivity of a prior known abnormality will be labeled MRD_{pos}.

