4.2 Inclusion Criteria

Subjects must meet all of the following criteria to be eligible for study participation:

- A. Both males and females \geq 61 years of age
- B. A clinical diagnosis of de novo, non-M3 acute myeloid leukemia (AML) confirmed by greater than 20% blasts in peripheral blood or on diagnostic bone marrow biopsy who have completed intensive induction chemotherapy and are confirmed in complete remission #1 (defined by $< 5\%$ myeloblasts on recovery BM biopsy, ANC $> 1000/\mu\text{L}$ and platelets $> 100 \times 10^3/\mu\text{L}$) and able to receive HiDAC consolidation #1
- C. Patients on the prospective arm must be willing to have labs/clinic visits at UF Health Shands approximately every 48 hours +/- 24 hours after discharge from chemotherapy admission to be included
 - If prospective subjects cannot be followed at the UF site then telephone visits are allowed to follow for toxicity and transfusions. Records can be requested from subject's local physician office.
- D. Written informed consent obtained from the subject and the subject agrees to comply with all the study-related procedures. For subjects on the historical arm, there will be a waiver of informed consent (as these patients may be deceased or not be available for retrospective consent).

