6. STUDY PROCEDURES

Written informed consent must be obtained prior to performing any study-specific evaluations or tests. Tests or evaluations performed as standard of care within the specified screening period, but prior to informed consent, may be accepted for this study and need not be repeated. Screening measurements below will be obtained within 60 days prior to registration into the study. **After registering a subject into this study, study treatment must begin within 30 days or subject will need to be re-screened:**

- Demographic data, including date of birth, gender, race, ethnicity and zip code
- Medical history, including h/o MDS or other conditions that could cause secondary or treatment-related AML or other conditions that may have major psychiatric or medical illness(es) that may impact if subject able to consent or be monitored for cerebellar toxicity
- Previous diagnostic assessments and treatment(s) for AML including regimens and dates
- Medications that may exclude subject (such as FLT3 inhibitors, e.g. midostaurin, sorafenib, gilteritinib, or any investigational FLT3 inhibitor as well as IDH1 and IDH2 inhibitors, e.g., ivosidenib, enasidenib or any investigational IDH inhibitor
- Bone marrow aspirate and/or biopsy for clinical classification, flow cytometry, cytogenetic classification, molecular markers, NGS for identification of commonly tested mutations in AML at diagnosis and at hematologic recovery after induction chemotherapy

- Hematology laboratory evaluations:
 - Complete blood count (CBC) including hemoglobin, hematocrit, white blood cell (WBC) absolute with differential, and platelet count
- Blood chemistry laboratory evaluations: serum creatinine
- Blood transfusions, growth factors, anti-infective medications, eye drops

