8.3 Replacement of Subjects

Subjects will be replaced if they have not received any doses of study drug prior to their withdrawal.

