9.2 Correlative Studies

We will compare the ACSS score for association with clinical endpoints using appropriate statistical tests as used in our previous work. Statistical analysis will be performed to compare overall-survival (OS), between ACSS groups using Cox regression and Fisher's exact test for toxicity endpoints and Wilcoxon test for association of ACSS score with duration or neutropenia/thrombocytopenia.

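### OS and LFS are timed from complete remission, but patients join either cohort only on reaching consolidation cycle 1, so described survival includes guaranteed event-free time

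*Combined protocol and SAP*

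**What the plan says.** **Time origin.** Section 2.3.2 states "Overall survival defined as the time from date of complete remission (CR) to death from any cause" and "Leukemia-free survival defined as time from CR to AML relapse or death, whichever comes first". The synopsis defines both endpoints in the same way.

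**Entry to the prospective cohort.** Under section 4.2 B, subjects must be patients who "are confirmed in complete remission #1" and are "able to receive HiDAC consolidation #1". Section 8.3 adds: "Subjects will be replaced if they have not received any doses of study drug prior to their withdrawal".

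**Entry to the control cohort.** Sections 3.1 and 12.2 identify controls as patients who received HiDAC on Days 1, 3 and 5 between 2/1/2017 and 2/1/2019.

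**Permitted interval.** Section 6 says "Screening measurements below will be obtained within 60 days prior to registration into the study", and the post-induction recovery marrow is among those measurements. After registration, "study treatment must begin within 30 days or subject will need to be re-screened". The Schedule of Events (section 6.1) instead heads the screening column as at most 60 days before Day 1.

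**Analysis.** Section 12.5 makes the exploratory endpoints descriptive. Section 9.2 plans to "compare overall-survival (OS), between ACSS groups using Cox regression". Neither section specifies delayed entry, a landmark or a Day 1 origin.

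**The concern.** A patient who died or was found to have relapsed between CR and consolidation Day 1 cannot appear in either cohort. Every patient who does appear is nevertheless credited with that interval as survival. This is guaranteed (immortal) time. It places a flat segment, of a length that varies by patient, at the start of each curve.

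The interval also says nothing about the schedule question, because the two schedules do not differ until consolidation begins. Section 2.3.2 states that OS and LFS are not expected to differ between cohorts, and the synopsis rationale hopes to adopt the condensed regimen as standard. Survival figures offered as reassurance should not include time in which failure was impossible by selection.

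**Working it through.** **1. The plan's own figure.** The documents give no survival rate, median or sample size for OS or LFS, so there is nothing to reproduce for these endpoints. The one sample-size statement (section 12.2) concerns neutropenia duration: 23 per group, difference 3 days, SD 4, one-sided alpha 0.05. It reproduces: 80.5% power by the exact noncentral t, 81.6% by the normal approximation, against 81% stated; 23/0.8 = 28.75, rounded up to 29. The present point does not touch it.

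**2. Longest permitted gap d from CR marrow to Day 1.**
- Section 6: 60 days before registration + 30 days after = 90 days.
- Schedule of Events: 60 days.

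These conflict. Two other places suggest shorter usual gaps. Footnote 3 of the Schedule of Events puts the screening marrow within 30 days after the start of induction. Section 12.3 dichotomises the delay from induction to consolidation cycle 1 at 40 days.

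**3. Size of the effect.** Let S(t) be survival from CR among all patients reaching CR. If only patients who survive to Day 1, at gap d, are included, an unadjusted curve from CR estimates S(t)/S(d). I assume S(t) = 0.5^(t/m), with median m of 12 to 24 months (not from the documents), t = 12 months, and d converted at 30.4375 days per month.

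| Assumed median | True 12-month OS | d = 30 days | d = 60 days | d = 90 days |
|---|---|---|---|---|
| 12 months | 50.0% | 52.9% (+2.9) | 56.0% (+6.0) | 59.3% (+9.3) |
| 18 months | 63.0% | 65.4% (+2.4) | 68.0% (+5.0) | 70.6% (+7.6) |
| 24 months | 70.7% | 72.8% (+2.0) | 74.9% (+4.1) | 77.0% (+6.3) |

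For a 10-day gap the excess is 0.7 to 1.0 points. Under a constant hazard the median is overstated by exactly d: 30/30.4375 = 1.0 month, or 90/30.4375 = 3.0 months. The same arithmetic applies to LFS with its own, also unstated, median.

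The table gives every patient the same gap. With gaps spread uniformly over 0-90 days and a median of 18 months, simulation gave 66.7% unadjusted against a true 63.0%, an excess of 3.7 points.

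**4. Does the remedy work?** In that simulation, delayed entry at Day 1 returned 62.9%, and Day 1 as time zero returned 63.0%.

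**5. ACSS Cox model.** I simulated 29 subjects in two ACSS groups, with true hazard ratio 2, medians of 12, 18 and 24 months, and gaps uniform on 0-30, 0-60 and 0-90 days, independent of ACSS (600 runs each). The median estimated hazard ratio differed by no more than about 0.02 between the CR origin, delayed entry and the Day 1 origin. The mean absolute change in log hazard ratio stayed below 0.05, against a sampling SD of 0.41 to 0.45.

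**The case against.** **Survival from CR among patients who reached consolidation is a legitimate quantity.** The protocol states its origin openly and applies it to both cohorts. This is correct as far as it goes: read conditionally, the curve is valid but has a flat start. The plan does not state that condition, and a reader would take the result as survival after remission.

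**Ninety days is not a typical gap.** This stands. It is the sum of two windows, the Schedule of Events contradicts it, and the 30-day marrow rule and 40-day cut-point point to shorter intervals. The 6-9 point figure is a ceiling. Typical inflation is probably 1 to 3 points, which is a judgement about the usual gap rather than a figure in the documents.

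**The cohort comparison need not be biased.** This also stands. Controls are selected on the same condition. A reader might infer that consent, screening and registration lengthen the gap in trial subjects and so flatter HiDAC 123. The documents give no gap for either cohort, and section 6 accepts standard-of-care tests done before consent. Even a 30-day difference would shift 12-month OS by only 2-3 points. By contrast, the 95% half-width for a difference with 29 per cohort is 1.96 × √(2p(1−p)/29), or 23 to 26 points at p = 70.7% and 50.0%, ignoring censoring.

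**The ACSS hazard ratio is barely affected.** It is tempting to say the Cox model is compromised because subjects are at risk before they could have an event. The check above shows a negligible effect when the gap is unrelated to ACSS.

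**Little depends on these endpoints.** They are descriptive, and no test of the cohorts, margin or stopping rule uses them. Nor are they the only long-term check, since relapse rate is also described in each cohort.

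**Conclusion.** The point holds as a modest upward bias in the described OS and LFS curves of both cohorts. It follows from the definitions and entry rules alone. For the stretch between registration and Day 1 in the prospective cohort it also relies on the replacement rule in section 8.3.

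Its size rests on assumptions the documents do not supply: exponential survival and a median of 12 to 24 months. On those assumptions 12-month OS is overstated by about 2-3 points for a 30-day gap, 4-6 for 60 days and 6-9 for 90 days, the last being a ceiling.

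The documents do not establish a false difference between cohorts, which would need unequal gaps, or material damage to the ACSS hazard ratio. The primary analysis and the sample size are unaffected. The change is worth making because it is cheap and removes a real bias from figures that will be reported.

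**What to change.** In the synopsis and section 2.3.2, define OS and LFS from Day 1 of HiDAC consolidation cycle 1 in both cohorts, and use the same origin in section 9.2 for consistency. Alternatively, keep CR as the origin and enter each patient into the risk set at Day 1 (delayed entry, left truncation).

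In either case, report the distribution of the CR-to-Day 1 interval by cohort, so that readers can see whether it differs. Reconcile the screening window in section 6 with the one in the Schedule of Events.

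The cost is a few sentences of wording. Cytarabine administration dates are already recorded under section 7.1, and no visit, sample or extra subject is needed. The downside of the Day 1 origin is that reported survival times become shorter by the CR-to-Day 1 interval and less directly comparable with literature measured from CR. Delayed entry keeps the CR time scale.

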3. STUDY DESIGN

3.1 Study Overview

This is a single center, open-label, non-randomized phase II study. Twenty nine (29) subjects are planned to be enrolled in this study. Each subject will be administered cytarabine 1000 mg/m² IV q12h x 6 doses on Days 1-3 in the hospital during the consolidation treatment phase. Subject may receive up to four consolidation cycles. Subjects will have laboratory and toxicity assessments as clinically indicated (at baseline, then daily while inpatient and ideally every 48 hours after hospital discharge +/- 24 hours until count recovery from each cycle). These subjects will be compared to 29 historical controls [matched by age (within 3 years), gender (male or female), PS (Karnofsky: 90-100, 70-80, or 50-60) and number of HiDAC cycles received] who received HiDAC 135 from the time period of 2/1/2017-2/1/2019.

Screening data will be reviewed to determine subject eligibility. Subjects who meet all inclusion criteria and none of the exclusion criteria and who have consented will be entered into the study. The following treatment regimen will be used for prospective arm: cytarabine 1000mg/m² IV q12h x 6 doses (Days 1-3) for up to four cycles.

Historical arm subjects will have received cytarabine 1000 mg/m² IV q12h x 6 doses (Days 1, 3, and 5) for up to four cycles from the time period of 2/1/2017-2/1/2019.

Total duration of subject participation will be up to six months from start of first consolidation cycle (each cycle is 28 days, but more time may be required allowing extra time for delayed count recovery in some patients); study participation will end when subject recovers neutrophils and platelets after last administered cycle of chemotherapy, is admitted for conditioning chemotherapy for HCT, dies, or withdraws consent (whichever comes first). However, subjects will be followed every 3 months (\pm 28 days) for up to 48 months after start of induction to determine long-term outcomes. Total duration of the study is expected to be 60 months.

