	lab) and based on the ACSS score classify into two groups having ACSS score ≥ 0 or <0). ACSS score will be evaluated for association with certain endpoints (duration of neutropenia, thrombocytopenia, RR and OS). Peripheral blood samples will be collected and analyzed through [name] lab at the University of Florida and NGS results will be used to calculate the ACSS score.
Study Design:	This is a non-randomized, open-label, single group phase II study for the prospective arm. These subjects will be compared to matched historical controls who received Day 135 consolidation for the primary and secondary objectives. Historical controls will be matched with prospective subjects for age (+/- 3 years), gender (male or female), Karnofsky PS (90-100/70-80/50-60), and number of HiDAC cycles received.
Accrual Goal:	A total of 29 subjects in HiDAC 123 arm. Data collected from these subjects will be compared to data from 29 matched historical controls who received standard HiDAC 135 consolidation.
Inclusion Criteria:	
Individuals eligible for study participation must meet the following criteria:
 
 A. Both males and females ≥ 61 years of age B. A clinical diagnosis of de novo, non-M3 acute myeloid leukemia (AML) confirmed by greater than 20% blasts in peripheral blood or on diagnostic bone marrow biopsy who have completed intensive induction chemotherapy and are confirmed in complete remission #1 (defined by < 5% myeloblasts on recovery BM biopsy (ANC $> 1000/\mu\text{L}$ and platelets $> 100 \times 10^3/\mu\text{L}$) and able to receive HiDAC consolidation #1. C. Patients on the prospective arm must be willing to have labs/clinic visits at UF Health Shands after discharge from chemotherapy approximately every 48 hours +/- 24 hours until neutrophil and platelet count recovery after each chemotherapy cycle per standard of care to be included. 
 - If prospective subjects cannot be followed at the UF site then telephone visits are allowed to follow for toxicity and transfusions. Records can be requested from subject's local physician office.

	
D. Written informed consent obtained from the subject and the subject agrees to comply with all the study-related procedures as stated above. For subjects on the historical arm, there will be a waiver of informed consent (as these patients may be deceased or not be available for retrospective consent).

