1.1 Acute Myeloid Leukemia Cancer Therapy

Acute myeloid leukemia (AML) is a rare type of cancer (1.1% of all new cancer cases); AML affects 4.3 people per 100,000 men and women per year.⁶ Patients undergo treatment to induce a complete remission if fit to receive chemotherapy. Once complete remission is confirmed after induction chemotherapy, AML patients receive consolidation chemotherapy. A standard AML consolidation regimen is HiDAC (cytarabine 1000-3000 mg/m² IV q12h on Days 1, 3, 5 every 28 days) x 3-4 cycles in USA.⁷ Many institutions use HiDAC as consolidation chemotherapy or as a bridge to hematopoietic stem cell transplantation. Dosing of cytarabine varies for treatment of AML; for consolidation, some regimens may include cytarabine 100-200 mg/m² continuous IV infusion Days 1-5 given in combination with anthracycline or HiDAC alone for 3-4 cycles. For induction regimens, often HiDAC is incorporated into various regimens, including cytarabine \geq 1000 mg/m² IV q12h x 8-12 doses. Doses depend on age, renal function, performance status and institution/provider. Generally, patients over the age of 60 years receive cytarabine 1000 mg/m² for HiDAC consolidation.⁸ UF Health Shands Hospital routinely uses cytarabine 1000 mg/m² IV q12h on Days 1, 3, and 5 up to 4 cycles (if tolerated) for standard chemotherapy consolidation in older AML patients. Jaramillo et al recently published results from two European trials showing that a modified consolidation regimen of HiDAC on Days 1, 2 and 3 reduced the duration of neutropenia and number of blood product transfusions in younger AML patients compared to standard HiDAC consolidation on Days 1, 3 and 5 with no adverse effects on long-term outcomes.¹ Dumas et al subsequently published a retrospective study of centers in France showing that adult patients age 18 to 60 years old with de novo or secondary AML

[figure not shown]

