6.2 End of Treatment Evaluations

The End of Treatment date will be the date the subject has met one of the following:

- 3-4 cycles of planned consolidation treatment
- Study withdrawal
- HCT conditioning
- Treatment ended earlier than planned (due to toxicity or physician discretion)
- Relapsed disease

All subjects will have the following procedures documented:

- Reason for end of treatment (relapse or transplant, etc.)
- Supportive care medications and transfusions if needed
- AE assessment
- Hematology laboratory evaluations (unless recovery was documented in a previous visit): complete blood count (CBC) including hemoglobin, hematocrit, white blood cell (WBC) including differential and platelet count
- Assessed for complete hematologic recovery
 - Reference Appendix C. ELN Guidelines

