6.3 Follow up Evaluations

Subjects will have follow-up visits for the evaluation of adverse events, labs, etc. per standard of care (after discharge from chemotherapy administration, generally every 48 hours +/- 24 hours until neutrophil and platelet recovery after each consolidation chemotherapy cycle). Patients will be evaluated prior to starting next chemotherapy cycle, then admitted for chemotherapy and monitored while inpatient.

If the subject is unavailable to travel to the institution (if situation changes from study inclusion criteria after subject starts first consolidation cycle), the visit may be made via telephone interview to review for adverse event resolution or the occurrence of any new adverse events, and outside labs reviewed if collected. Additionally, medical records may be requested with permission of the subject to complete remote visit reporting e.g., if admitted to an outside institution due to complications of chemotherapy.

If the subject is at the treating facility and the physician decides to hold, reduce, or omit the dose completely, the following procedures should be performed:

- Document reason for delay, decreased or missed doses
- AE assessment
- Hematology laboratory evaluations: complete blood count (CBC) including hemoglobin, hematocrit, white blood cell (WBC) with differential and platelet count

If study therapy is discontinued before planned, disease assessments will be performed as clinically indicated, such as suspicion of relapse. Reason for discontinuation should be documented, e.g., relapse, proceeding to HCT, unexpected toxicity/poor tolerance of chemotherapy, etc. Subjects will continue to be followed every 3 months (\pm 28 days) for survival data up to 48 months after induction chemotherapy is started, or until relapse or death (whichever comes first). Following discontinuation of study therapy for any reason, report the date as appropriate (date of confirmed relapse, date of death, date of start of HCT conditioning, or recovery from last planned or unplanned cycle).

If a subject becomes unreachable during the course of the study, the investigator or study team will make a reasonable effort to contact the subject and document each attempt. If these attempts are not successful, the subject may be declared "lost to follow up." For subjects lost to follow-up, the termination date will be the date of last contact with the subject.

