8.2 Criteria for Study Treatment Discontinuation

Subjects who discontinue participation in the clinical study on their own or subjects who are withdrawn by the investigator, for reasons other than completion of treatment, proceeding to HCT, relapse or toxicity, will be defined as premature withdrawals. The end of treatment data will be collected if available at last visit if confirmed relapse, death, or proceeding to HCT. For those with toxicity that end before planned last cycle, data will be collected up to the end of treatment date and AE data will be collected until 28 days following the most recent dose of study treatment or initiation of a new chemotherapy regimen (whichever comes first).

Subjects will be followed for long term data every 3 months (\pm 28 days) until relapse, death or until 48 months after induction therapy (whichever comes first).

A subject will be discontinued from protocol therapy under the following circumstances:

- Any adverse event which, in the Investigator's opinion, requires termination of the chemotherapy
- Disease relapse
- If subject proceeds to allogeneic HCT
- The subject uses illicit drugs or other substances, or takes part in activities that may, in the opinion of the Investigator, have a reasonable chance of contributing to toxicity or otherwise interfering with results
- The subject is lost to follow-up
- Death
- Development of an intercurrent illness or situation which would, in the judgment of the investigator, affect assessments of clinical status and study endpoints to a significant degree

The Investigator will make every reasonable effort to keep each subject in the study unless it is in the subject's best interests to discontinue participation. If a subject is removed from the study or declines further participation, all EOT evaluations should be performed if the subject is willing and able to be assessed. A description of the reason(s) for withdrawal from the study must be recorded on the case report form (CRF). The Investigator should also ensure that all subjects are followed up for survival status after the Final Visit.

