12.2 Sample Size Justification

This is a prospective single group study to determine the duration of neutropenia after consolidation chemotherapy with HiDAC 123. A historical control group will be selected by identifying patients who received cytarabine 1000 mg/m² IV q12h D135 from 2/1/2017-

2/1/2019 by propensity matching factors: age (+/- 3 years), gender (male or female), Karnofsky PS (90-100/70-80/50-60), and number of HiDAC cycles. The hypothesis is that patients with HiDAC123 treatment schema have a shorter duration of neutropenia after consolidation chemotherapy, compared to matched historical controls who received HiDAC 135. Group sample sizes of 23 subjects from a prospective cohort and 23 subjects from historical baseline group will achieve 81% statistical power to reject the null hypothesis of equal means when the population mean difference in neutropenia duration is three days (16 vs. 19 days) with a standard deviation for both groups of four days and statistical significance level (alpha) of 0.05 using a one-sided, two sample, equal-variance t-test. Including 20% drop out rate, we will accrue 29 subjects per cohort.

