12.3 Analysis of Primary Endpoint

When the required assumptions are met, duration of neutropenia will be analyzed by a one-sided, two sample, equal-variance t-test. If the normal distribution and equal variance are not validated, the corresponding non-parametric method will be used. Primary analysis will be for cycle 1 of consolidation only. Other cycles will be recorded and use descriptive statistics. Further, multivariable linear regression model of the neutropenia in days with group as the primary independent variable of interest will be fitted, while adjusting for some potential confounding variables, including AML type (WHO and FAB), documented infection in consolidation #1 (yes or no), ELN risk category (favorable, intermediate, high) and MRD positivity (yes or no), WBC at diagnosis (<50,000 or \geq 50,000), delay between induction course and consolidation #1 (less than or more than 40 days), allogeneic HCT (yes or no).

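### Historical controls are matched on the number of HiDAC cycles received, which is settled only after the cycle-1 primary outcome, so the match can bias the primary comparison

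*Combined protocol and SAP*

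**What the plan says.** Three places define the match. The synopsis (Study Design) lists age, gender, "Karnofsky PS (90-100/70-80/50-60), and number of HiDAC cycles received", and uses these controls for both the primary and the secondary objectives. Section 3.1 repeats the list, ending "and number of HiDAC cycles received] who received HiDAC 135 from the time period of 2/1/2017-2/1/2019". Section 12.2 selects controls "by propensity matching factors: age (+/- 3 years), gender (male or female), Karnofsky PS (90-100/70-80/50-60), and number of HiDAC cycles".

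Section 12.3 limits the primary test: "Primary analysis will be for cycle 1 of consolidation only". Section 3.1 allows up to four cycles.

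On what determines the number of cycles, section 1.1 describes local practice as "up to 4 cycles (if tolerated) for standard chemotherapy consolidation in older AML patients". Section 6.2 includes among the end-of-treatment events "Treatment ended earlier than planned (due to toxicity or physician discretion"). Section 6.3 gives as reasons for discontinuation "relapse, proceeding to HCT, unexpected toxicity/poor tolerance of chemotherapy, etc". Section 8.2 provides for early stopping: "For those with toxicity that end before planned last cycle". For slow count recovery, sections 3.1 and 7.1 allow extra time or modified administration and do not name it as a reason to stop.

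Nothing limits the cycle match to later-cycle or secondary endpoints, explains why it is needed for cycle 1, or plans a sensitivity analysis without it.

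**The concern.** A matching factor should be fixed before the outcome it is meant to protect. Cycles not yet given cannot confound neutropenia in cycle 1, so this factor removes no bias from the primary comparison. It can add bias.

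The study's hypothesis is that HiDAC 123 shortens neutropenia. If patients with long cycle-1 neutropenia tend to receive fewer cycles, HiDAC 123 patients will tend to receive more. Each is then paired with a HiDAC 135 control who also received many cycles, and who is therefore likely to have recovered quickly. Part of the effect under test is matched away.

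If regimen or era also shifts the cycle count (controls are from 2017-2019, prospective patients later), the bias can go in either direction, including toward a false positive. The regression in section 12.3 is no remedy, because nothing indicates that it uses a different control set.

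There are two practical consequences. A control cannot be chosen until the prospective patient's last cycle is known. And under exact matching, an extra factor can only keep or shrink the pool of eligible controls, whose size is not given.

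**Working it through.** **1. The plan's own figures.** Section 12.2 gives means of 16 and 19 days, SD 4, one-sided alpha 0.05, a pooled-variance t-test and 23 per group.

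- Noncentrality = 3 / (4 × √(2/23)) = 3 / 1.180 = 2.54 on 44 df, so power is 80.5%. The normal approximation gives 81.6%. The stated 81% is reproduced.
- 23 / 0.80 = 28.75, so 29 per cohort, as stated.
- At 29 per group, 3 / (4 × √(2/29)) = 3 / 1.050 = 2.86 on 56 df, so power is 88.0%.

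**2. Order of events.** Cycle-1 neutropenia is observed, later cycles are given or not, and then the cycle count is known. The match uses the last item and the primary test uses the first. This follows from the text and needs no assumption.

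**3. Illustration of size.** The documents give no link between neutropenia and cycle count, so all slopes here are assumptions. Cycle count (1 to 4) follows an ordinal logit in cycle-1 duration, with an assumed control distribution of 30/30/25/15%. Controls are drawn within the case's cycle stratum, with 40,000 simulated trials per cell. A slope of −0.10, −0.20 or −0.30 log-odds per day means odds of more cycles lower by 1 − e^−0.10 = 10%, 1 − e^−0.20 = 18% or 1 − e^−0.30 = 26% per extra day.

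Same rule in both groups, true difference 3.0 days:

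| Slope | Matched difference (days) | Power, n=23 | Power, n=29 | Type I error, n=23 |
|---|---|---|---|---|
| 0 | 3.00 | 80.4% | 87.9% | 5.1% |
| −0.10 | 2.87 | 77.2% | 86.2% | 4.5% |
| −0.20 | 2.52 | 68.7% | 78.9% | 3.7% |
| −0.30 | 2.16 | 57.7% | 67.6% | 2.7% |

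With the same rule there is no bias under the null. Type I error falls below 5% because matched pairs are positively correlated and the unpaired test ignores this.

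**4. Cycle count also shifted by regimen or era** (slopes −0.10 / −0.20 / −0.30):

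- HiDAC 123 patients with half the odds of more cycles: a true zero difference appears as 0.31 / 0.54 / 0.65 days. Type I error is 7.9 / 9.8 / 9.9% at n=23 and 8.4 / 10.7 / 11.0% at n=29.
- HiDAC 123 patients with twice the odds: a true 3.0 days appears as 2.55 / 1.99 / 1.53 days. Power at n=23 is 68.6 / 51.0 / 34.0%.
- With slope 0, either shift leaves 3.00 days and about 5% type I error.

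**5. A second model.** Here the link is expressed as a correlation rho between duration and a latent tolerance score, with 2,000,000 patients per arm and controls reweighted to the HiDAC 123 cycle distribution. For rho 0.1 / 0.2 / 0.3 / 0.5 / 0.7, a true 3.0 days appears as 2.98 / 2.90 / 2.78 / 2.39 / 1.85 days, with power at n=23 of 80 / 78 / 75 / 64 / 46%. If HiDAC 123 lowers tolerance by 0.5 SD through another route, then at rho 0.3 a true 3.0 days appears as 3.28 days, and one-sided rejection under the null is about 11%. If cycle count depends only on patient frailty, and not on the regimen or its effect on duration, there is no bias (3.00 days).

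**The case against.** The strongest reply is that the required link is not documented. Slow recovery leads to extra time or modified administration, not to stopping. Relapse, transplant and completion of the planned cycles are competing reasons for the final count, and the toxicity wording is not specific to neutrophils. This stands as a limit on certainty: the size is unknown and may be nil.

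The steeper slopes are also strong assumptions. Over seven extra days, −0.30 per day cuts the odds of more cycles by about 88% (e^−2.1 = 0.12). At −0.10, already a halving per week (e^−0.7 = 0.50), the loss is about three power points at n=23. At −0.05 the difference is 2.95 days with 79% power. At the weak end, then, the effect is small.

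In the most plausible direction the error is conservative, so a positive result would survive. The inflated type I error needs a second unsupported assumption about regimen or era, and section 12.6 expects no additional adverse effects from the schedule change. Other differences between eras would remain whatever is done with this factor.

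Finally, section 12.2 speaks of propensity matching, and a looser match could give less bias than the exact strata simulated. Exact matching on cycles is, however, the natural reading of the synopsis and section 3.1.

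These points limit the size claimed. None of them gives a reason to keep the factor for a cycle-1 endpoint.

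**Conclusion.** The concern holds. The plan matches the primary comparison on a variable settled after the primary outcome, and its own text makes a link between the two plausible. The direction is most plausibly toward no difference, but this is not guaranteed.

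The size cannot be determined. Under assumed slopes with a common rule, the loss ranges from nothing to about 0.8 days of a true 3.0, with power at 23 per group between 80% and 58%. Type I error rises above 5% only if cycle count also differs by regimen or era. The figures assume exact matching on cycles and the plan's SD of 4 days.

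Because the factor offers the cycle-1 endpoint no benefit and is cheap to remove, it should be fixed. Confidence that it matters materially in this trial is medium.

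**What to change.** For the primary analysis, remove the number of HiDAC cycles from the matching factors in the synopsis, section 3.1 and section 12.2. Match only on what is known before cycle 1: age, gender and Karnofsky PS. Report cycles received by group as a descriptive result, and report multi-cycle secondary endpoints per cycle or by cycle number.

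If total-course outcomes such as total length of stay (section 2.2.2) are to be compared at equal exposure, define a separate cycle-matched set for those endpoints only, within the exploratory comparisons that section 12.4 already permits.

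The core change is wording in three places, with no new data; power stays at 80.5% with 23 per group and accrual at 29 per cohort. The downside is that total-course outcomes are no longer compared at equal cycle counts unless the optional second set is kept. That set could require extra chart abstraction if it draws on different patients.
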